Postoperative pain that persists beyond the normal time for tissue healing is increasingly recognized as an important complication after various types of surgery. According to the International Association for Study of Pain, CPSP is defined as the persistence of pain at surgical site or referred area, at least 3 months following the surgical procedure.⁹ CPSP is common after cardiac surgery. The reported incidence was 28% to 56% up to 2 years postoperatively.¹⁰⁻¹² Several mechanisms have been involved in the development of chronic pain after sternotomy. These include dissection, nerve entrapment by sternal wires, sternal retraction, ribs fractures, and intercostal neuralgia as a consequence of nerve damage during dissection of the internal mammary artery during coronary artery bypass graft (CABG).²⁻³ In addition, poorly controlled pain has been a general risk factor for the development of CPSP. All can stimulate the release of pro-inflammatory cytokines which sensitize the afferent nociceptive fibres to cause chronic pain. CPSP has the potential to impact daily functioning and quality of life of patients, as well as increasing the healthcare costs. CARDpain study reported that among those with CPSP, over 50% had significant pain-related interferences with activities of daily living (family and home responsibilities, recreation and employment) at 3, 6 and 12 months following cardiac surgery.¹³ Therefore, apart from optimal acute pain control, it is equally

important to prevent and manage CPSP, to ensure better satisfaction and quality of lives for our patients.

CHALLENGES IN PAIN MANAGEMENT

Intravenous opioids such as fentanyl and morphine have been the mainstay of perioperative analgesia for cardiac surgery, either by intermittent boluses or through a patient-controlled device. The primary problem with this mechanism of delivery is that significant fluctuations in serum opioid concentrations can occur, resulting in effects which range from inadequate analgesia to overdose and respiratory depression. These peaks and troughs of analgesia that occur with intermittent opioids administration may explain the suboptimal pain control during the initial postoperative period. In contrast to intermittent administration of short-acting opioids such as morphine and fentanyl, a single dose administration of methadone can be considered. Methadone was conventionally used in cancer and chronic pain management. It can be administered via oral, intravenous, and other parenteral routes. Despite being an often-used alternative to morphine, it remains relatively invisible in perioperative settings. Methadone is a unique opioid that may provide several important potential benefits for surgical patients in the perioperative period. It is a potent mu receptor agonist with a rapid onset and longest half-life (24-36 hours) of the clinically used opioids. According to a pharmacokinetic study,¹⁴ central nervous system effect site methadone concentration rapidly equilibrates with plasma concentrations, evidenced by a short lag time between plasma concentrations and effects ($t_{1/2}k_{e0}$ 4min). This is comparable to the rapid onset and effect compartment equilibration of fentanyl and sufentanil (5-6min), and in contrast the slow onset time of morphine, where $t_{1/2}k_{e0}$ has been reported to exceed 4 hours.¹⁵ In addition, as reviewed in an editorial, when methadone is administered at a dose of 20mg or higher, the duration of analgesia approximates the half-life of 24-36 hours. Therefore, a single intravenous dose 20mg administered to an adult at induction of anaesthesia should provide a rapid onset and significant pain relief up to 1-2 days postoperatively, which is the period reported to have the highest pain score after cardiac surgery. Methadone is also a N-methyl-D-aspartate (NMDA) receptor antagonist. It has been reported to possess anti-hyperalgesic and anti-allodynic properties, that is important in preventing pain sensitization and the development of CPSP,¹⁶⁻¹⁷ which is of high risk in cardiac surgical patients.

SIDE EFFECTS OF METHADONE

Methadone shares the same opioid-related side effects as with many other opioids such as nausea and vomiting, drowsiness and respiratory depression. According to a meta-analysis in 2020 which

included seven randomized controlled trials on intraoperative use of intravenous methadone¹⁸, four studies reported no adverse events. One study reported that the patients who received intraoperative methadone experienced more sedation compared to control group at 24 hours after surgery. One study reported that the intraoperative morphine group had more sedation compared to methadone group during the postoperative period. Methadone was not shown to have a higher incidence of postoperative nausea and vomiting compared to the morphine group. Methadone has been reported to be associated with cardiac conduction abnormalities such as QT prolongation, QT interval dispersion and cardiotoxicity (Torsade de pointes).¹⁹ However, most of the cardiac-related side effects were seen in patients on prolonged or maintenance treatment with methadone. Significant dose-dependent QTc prolongation usually occurs at a high dose of methadone. A single injection of intravenous methadone at low dose is unlikely to result in significant cardiotoxicity. No cardiac disturbances were reported from the meta-analysis.¹⁸

GAPS IN THE LITERATURES

Only a few trials have studied intravenous methadone as an analgesic in surgical patients, in particular, there have not been many studies in the field of cardiac anaesthesia. A randomized controlled trial done by Murphy et al showed intraoperative methadone to be superior to fentanyl for patients undergoing cardiac surgery.²⁰ Methadone was demonstrated to reduce morphine consumption in the first 24 postoperative hours and improved pain scores at 12h after extubation compared to patients receiving fentanyl. There was 40% reduction in morphine requirement during the first 24h after extubation, and the severity of postoperative pain was decreased by 30-40% during the first three days after cardiac surgery. There was only one study comparing the analgesic efficacy between methadone and morphine given at the time of induction in cardiac surgical patients.²¹ Methadone was shown to reduce opioid requirement at 24h postoperatively and significantly reduce the incidence of postoperative nausea and vomiting. So far there has not been any studies on using methadone for cardiac surgery in Chinese populations, and none on the role of methadone for prevention of chronic post-surgical pain in cardiac surgical patients. Substantial literatures have demonstrated the ethnic differences in pain perception and endogenous pain modulation is postulated to be a mechanism for ethnic differences. Studies comparing Caucasians and Asians, such as Chinese and Indians, generally demonstrated lower pain tolerance in Asian populations.²²⁻²³ The primary aim of this study is to evaluate the use of methadone on acute and chronic pain control after open cardiac surgery, compared with conventional opioid-based approach using morphine and fentanyl.

METHODS/DESIGN

Study population and design

This is a single-centre, double-blinded, pilot randomized controlled trial conducted at Prince of Wales Hospital, a university teaching hospital with 1650 beds in Hong Kong. All elective cardiac surgical patients will be admitted to a 23-bed ICU for early postoperative care and monitoring with 1:1 nursing at all times, with an expectation of discharge from ICU to a high-dependency cardiac ward within 24 hours after surgery. Currently 350-400 adults undergo elective coronary artery bypass graft and/or valvular surgery each year.

Randomization and concealment

Patients will be randomized to receive either methadone 0.2mg/kg (maximum dose 20mg) or equipotent dose of morphine, adding to a syringe containing saline made up to 50ml in total, by drawing sequentially numbered, coded sealed, opaque envelopes each containing the group assignment of either methadone or morphine group. The sealed envelopes for randomization will be prepared by a third party who takes no further part in the study. The study syringes containing the drug solution will be prepared by a nurse not involved in the study with blind labelling. The primary care team, blinded to the group allocation, will perform all surgical procedures using standardized techniques. Anaesthetists and nurses blinded to group allocation will record data intraoperatively, in ICU, and at regular intervals in the cardiac wards.

Eligibility criteria

We will include adult patients age 18 or older, undergoing elective coronary artery bypass graft (CABG), valve repair/replacement, or combined CABG valve procedure via sternotomy, with an expected extubation within 12 hours of surgery. The exclusion criteria include emergency surgery, aortic surgery, redo surgery, preoperative renal failure requiring renal replacement therapy or creatinine clearance <30ml/min (calculated by Cockcroft-Gault formula), liver dysfunction (liver enzymes twice upper limit normal), LVEF <40%, requirement of mechanical hemodynamic support in perioperative period, history of chronic pain or who regularly used pain medications (except paracetamol and non-steroidal anti-inflammatory drugs), history of psychiatric illnesses or illicit drug use, intraoperative use of remifentanil and unable to provide informed consent.

Anaesthesia and interventions

All patients will receive standard monitoring for cardiac surgery. General anaesthesia will be induced with midazolam 0.01-0.05mg/kg, fentanyl 2-5mcg/kg and rocuronium 0.5-1mg/kg to facilitate intubation with single-lumen cuffed endotracheal tube. Anaesthesia will be maintained with sevoflurane and propofol infusion that target Bispectral Index 40-60. The study drug (either methadone 0.2mg/kg or morphine at equipotent dose) in blind labelling will be administered at time of induction by intravenous infusion over 30 minutes. No further morphine will be given throughout the operation. No other analgesics (paracetamol, non-steroidal anti-inflammatory agents, dexmedetomidine, ketamine), steroids or antiemetics will be given intraoperatively. Patient-controlled analgesia (PCA) morphine protocol will be prescribed to patients for 72 hours after operation for postoperative analgesia. Oral analgesics including paracetamol 1g every 6 hours and dihydrocodeine 30mg three times a day will be prescribed by parent surgical team. At the end of the operation, the patients will be kept sedated with propofol infusion to ICU. Propofol infusion will be stopped upon admission to ICU to facilitate weaning from ventilator. Adaptive Support Ventilation (ASV) is used in ICU for weaning which adjusts the ventilation parameters depending on the patient's lung mechanics and effort. Pain will be assessed by nurses in ICU at 4h after stopping sedation, then once every 2h. Upon extubation, patient will be assessed the pain score and the level of sedation at 15min, 8h, 12h, 24h, 48h and 72h. 1mg morphine will be administered via PCA to patients if pain of more than mild severity was noted. Any nausea or vomiting, and use of rescue antiemetics will be documented.

Outcome measures

Primary outcomes

The most intense pain typically occurs in the first 2-3 days after open heart surgery, leading to greater need for analgesia during this period. The primary outcome will be set at 72-hour time frame based on the postoperative morphine consumption.

Secondary outcomes

Key secondary outcomes include the postoperative pain scores measured by numerical rating scale (NRS) represented as AUC at rest and movement; the time successfully weaned to spontaneous breathing according to ASV; patient satisfaction score to pain within 72h after the operation; time to first morphine rescue; side effects of opioids including the number of episodes of postoperative nausea and vomiting; time to first bowel movement; the recovery from surgery in terms of length of ICU and hospital stay; and chronic postsurgical pain at 3 and 6 months assessed using the Douleur Neuropathique en 4 questionnaire (DN4). It is a ten items questionnaire and the Mandarin Chinese

version has been validated in previous study.²⁶ Each item of DN4 is assigned a score of 0 when the participant answered ‘no’ and a score of 1 when the participant answered ‘yes’. The total DN4 score ranges from 0 to 10, and a score ≥ 4 indicates a diagnosis of neuropathic pain.²⁷⁻²⁸

Data collection

Patients will be screened the day before operation for eligibility. Eligible patients will be given the patients’ information sheets regarding the main aspects of the trial. Research nurses will then discuss with the patients in light of the information provided in the information sheets. Written informed consent will be obtained from patients willing to participate in the trial. All data is collected by research team members blinded to group assignment. Patient demographics and body mass index will be recorded. The time weaned to spontaneous breathing on ASV will be recorded. At 15min after tracheal extubation and at 8h, 12h, 24h, 48h and 72h post-extubation, pain score at rest and on coughing will be quantified using Numerical Rating Scale (NRS) from 0 to 10. Zero represents no pain at all while 10 points represents the worst pain ever. The time to first morphine rescue (in minutes after surgery) will be measured. The level of sedation will be measured using the Ramsay Sedation Scale (1 = anxious, agitated or restless, or both; 2 = co-operative, oriented and tranquil; 3= respond to command only; 4 = exhibit brisk response to light glabellar tap or loud auditory stimulus; 5 = exhibit sluggish response to light glabellar tap or loud auditory stimulus; 6 = exhibits no response), episodes of nausea and vomiting, and whether antiemetics are prescribed will also be recorded at the above time points. At the same time, patients will be asked to rate the overall satisfaction with pain management on a verbal analogue scale (0 = worst possible, 100 = best possible).

The Douleur Neuropathique en 4 questionnaire (DN4)²⁶ will be used to evaluate the presence of neuropathic pain at 3 and 6 months after surgery.

The following medical and surgical data during the hospital stays will be extracted from patient charts:

1. Patient demographics (age, gender, EuroScore)
2. Type of surgery
3. Duration of surgery and duration of cardiopulmonary bypass
4. ASV time to spontaneous breathing
5. Total morphine consumption at 24 and 72 hours after surgery
6. Episodes of nausea and vomiting, and use of rescue antiemetics
7. Length of ICU and hospital stay

		STUDY PERIOD									
		Post-allocation									
TIMEPOINTS	Enrolment	Baseline	OT	4h stop sedation	15min extubate	12h extubate	24h extubate	48h extubate	72h extubate	3-month postop	6-month postop
ENROLMENT:											
Eligibility screen			X								
Informed consent			X								
Demographic data			X								
Comorbidity data			X								
EuroScore			X								
Allocation			X								
INTERVENTIONS											
Intraoperative methadone				X							
Intraoperative morphine				X							
OUTCOMES:											
Ramsay sedation scale				X	X	X	X	X	X		
NRS score				X	X	X	X	X	X		
ASV time to spontaneous breathing					X						
DN4										X	X
Time to first morphine rescue						X	X	X	X		
Postoperative morphine consumption						X	X	X	X		
Patient satisfaction						X	X	X	X		
Use of rescue antiemetics						X	X	X	X		
Nausea/vomiting						X	X	X	X		
Time to first bowel movement						X	X	X	X		
ICU and hospital stay									X		

Figure 1 Assessments overview. NRS, numerical rating scale; ASV, adaptive support ventilation; NPQ, Neuropathic Pain Questionnaire; HK-PCS, Pain Catastrophizing Scale Hong Kong version.

Blood sampling for methadone level

Venous blood samples (5ml) will be obtained at 0, 1, 2, 4, 6, 8, 10, 12, 24, 48, 72 and 96 hours after administration of methadone. Plasma concentration of methadone will be determined by LC-MS/MS (ESI pos). The internal standard (7-dimethylamino-5,5-diphenyl-4-octanone, 2.5ng) will be added to plasma (0.5ml), which will be acidified and then processed by SPE (Waters Oasis MCX cartridges).

Sample size calculation and statistical methods

The sample size is calculated using G*Power software version 3.1.9.3 (Kiel University, Kiel, Germany), and based on postoperative morphine consumption at 24 hours, which is the primary outcome variable. Because there was no randomized controlled trial on use of methadone in cardiac surgery in Asian population, a pilot study (50 patients) was conducted from cardiac surgical patients in Prince of Wales Hospital, Hong Kong. The mean (SD) postoperative morphine consumption at 24 hours was 21.5 (8.2) mg in patients receiving methadone, whereas that for morphine group was 30.3 (14.0) mg. With an alpha probability of 0.05 and a power of 90%, a sample size of 34 patients in each group will be needed. Assuming 15% drop-out rate, the sample size is increased to 86 patients. The primary analyses will be performed on a modified intention-to-treat basis. Patients will be analysed according to their randomized allocated groups but will be excluded from the analysis if they do not adhere to the protocol after randomisation. Categorical data are reported as numbers and percentages. Continuous variables are reported as mean (standard deviation) or median (interquartile range) as appropriate after checking for normality using the Shapiro-Wilk's test. Comparison of continuous data is performed by Student's *t* test and by Mann-Whitney U test for non-normally distributed data. Chi-square test is used to compare groups with categorical variables. Level of significance is set at P<0.05. SPSS 27.0 software (IBM Corp, Armonk, NY) will be used for data analysis.

DECLARATIONS

Consent to participate

All participants will provide written informed consent. All research will be conducted in accordance with the Declaration of Helsinki and all other relevant guidelines and regulations.

Consent for publication

Not applicable

Competing interests

The authors declare that they have no competing interests.

Funding

This work was funded by the Health and Medical Research Fund from the Health Bureau of the Government of HKSAR (Reference number: 10211156), and internally supported by the Department of Anaesthesia and Intensive Care, The Chinese University of Hong Kong. This funding has no role in the design of this study and will not have any role during its execution, analyses, interpretation of the data, or decision to submit results.

REFERENCES

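### Two exclusion criteria are not limited to what is known before randomisation, so treated patients can be removed from the primary analysis because of later events

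*Protocol*

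**What the plan says.** The Protocol's Eligibility criteria section lists "intraoperative use of remifentanil" and "requirement of mechanical hemodynamic support in perioperative period" among the exclusions, without any qualifier such as planned, expected or preoperative.

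The timing comes from three other sections:

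- Data collection: "Patients will be screened the day before operation for eligibility".
- Randomization and concealment: allocation is made "by drawing sequentially numbered, coded sealed, opaque envelopes each containing the group assignment of either methadone or morphine group", and the blinded syringe is then made up according to arm.
- Anaesthesia and interventions: the study drug "will be administered at time of induction by intravenous infusion over 30 minutes".

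The section on sample size and statistical methods defines the analysis set: "The primary analyses will be performed on a modified intention-to-treat basis". Patients are kept in their allocated groups but "will be excluded from the analysis if they do not adhere to the protocol after randomisation".

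**The concern.** An eligibility criterion should be decidable before the envelope is drawn. As worded, both criteria also cover events during the operation, and the second covers events after it as well. By then the patient has been randomised and has received the study opioid.

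If such a patient is then treated as ineligible or non-adherent, the analysed groups are no longer the randomised groups. Extra intraoperative opioid may be given when analgesia is judged insufficient, and the haemodynamic course may differ between opioids. Either event could therefore depend on the arm, and either could be related to postoperative morphine consumption, which is the primary outcome. Blinding of the care team does not remove this problem, because selecting on a consequence of treatment can bias a comparison even when nobody knows the allocation.

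Correcting the modified intention-to-treat sentence alone would not be enough, because the same patients could still be taken out as never having been eligible.

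**Working it through.** **Order of events.** Screening is on the day before surgery. The envelope is drawn and the syringe prepared before induction. The study drug runs over 30 minutes from induction, and the operation and intensive care follow. The criteria sort as follows:

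| Situation | Known before the envelope is drawn? |
|---|---|
| Remifentanil planned as part of the technique | Yes |
| Remifentanil given during the operation without a prior plan | No |
| Mechanical support in place or planned before surgery | Yes |
| Mechanical support first needed during or after surgery | No |

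The same section words other criteria so that they can be settled beforehand: early extubation is framed as an expectation, and renal failure as a preoperative condition. The two criteria at issue lack any such limit.

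**Route out of the analysis.** For remifentanil there are two routes. It is a listed exclusion. It may also fall under the ban on other intraoperative analgesics in Anaesthesia and interventions. The bracketed list there does not name it, but if that list is only illustrative, its use is non-adherence and the statistical section removes the patient. For mechanical support only the eligibility route is clear, because needing support is a clinical event and not plainly a failure to adhere. No sentence in the Protocol keeps either kind of patient in.

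**Possible size.** The Protocol gives no figure on this point to reproduce, so this is an illustration with assumed removal rates.

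Inputs from the sample size section: 24-hour morphine consumption of 21.5 (SD 8.2) mg on methadone and 30.3 (SD 14.0) mg on morphine; planned difference 30.3 − 21.5 = 8.8 mg. Assumed: a fraction p of an arm is removed, and the mean of those removed lies k SDs above their arm's mean, with k = 0.5 or 1.

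The retained mean of an arm falls by p/(1 − p) × k × SD. The planned difference shrinks by the morphine fall minus the methadone fall.

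| Removed, methadone / morphine | Fall at k = 1, methadone | Fall at k = 1, morphine | Shift, k = 1 | Shift, k = 0.5 | Share of 8.8 mg |
|---|---|---|---|---|---|
| 5% / 5% | 0.0526 × 8.2 = 0.43 | 0.0526 × 14.0 = 0.74 | 0.31 mg | 0.15 mg | 2–3% |
| 2% / 10% | 0.0204 × 8.2 = 0.17 | 0.1111 × 14.0 = 1.56 | 1.39 mg | 0.69 mg | 8–16% |
| 5% / 15% | 0.0526 × 8.2 = 0.43 | 0.1765 × 14.0 = 2.47 | 2.04 mg | 1.02 mg | 12–23% |

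With 86/2 = 43 patients per arm, 2%, 5%, 10% and 15% are about 1, 2, 4 and 6 patients.

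In every row the observed methadone benefit gets smaller, because above-average users leave mainly the morphine arm. If those removed were below-average users, k would be negative and the same shifts would enlarge the benefit. That could happen with patients kept sedated or ventilated, who cannot press a patient-controlled device.

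**The case against.** **The criteria can be read as planned status.** A reader might infer that both criteria can be known only after study drug. The text does not support that: support already in place or planned, and remifentanil chosen in advance, can be known at screening. This stands, and it makes the defect one of unrestricted wording. The wording still covers later events, and nothing limits it.

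**Removal is not stated outright.** A reader might infer that the Protocol orders these patients to be dropped. No sentence says that a patient found to meet an exclusion criterion after randomisation leaves the analysis. For mechanical support the step is an inference. For remifentanil it is more direct, but it then overlaps with the general rule on non-adherence.

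**An effect of treatment is not shown.** The Protocol does not say why remifentanil would be used. Its section on side effects regards significant cardiotoxicity from a single low dose as unlikely and notes that the cited meta-analysis reported no cardiac disturbances. Blinding also rules out an arm-aware choice of remifentanil. Differential removal is therefore plausible but not demonstrated.

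**The larger shifts come from the assumptions.** The 8–23% range needs three- to five-fold differences in removal between arms. Nothing in the Protocol suggests this in an elective population without redo surgery and with reduced ejection fraction excluded. The SDs are 24-hour figures, whereas the Primary outcomes section uses a 72-hour time frame. These points stand, and the larger figures should not be used to measure importance.

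**Conclusion.** The point holds as a fault of wording and of the analysis set. Read together, the eligibility and statistical sections permit removal of treated, randomised patients on events that arise after allocation and that the study opioid could plausibly affect. This is clearest for intraoperative remifentanil. For mechanical support it is inferred and concerns only support first needed during or after surgery.

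The size and direction of any bias cannot be determined from the Protocol. Under equal 5% removal of above-average users the shift is about 0.15 to 0.3 mg, which is negligible against 8.8 mg. About 1 to 2 mg, towards a smaller methadone benefit, arises only under the assumed strongly unequal removal of such users. It would be wrong to conclude that the primary result will be materially biased, or biased in favour of methadone. The reason to act is that the protection of randomisation is given up without need and can be kept at little cost.

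**What to change.** 1. **Eligibility criteria.** Word both criteria by status known before the envelope is drawn: remifentanil planned for the operation, and mechanical support present or planned before surgery.
2. **Statistical methods.** Keep every randomised patient who received study drug in the primary analysis, in the allocated arm, whatever happens later. Record later remifentanil use or mechanical support as deviations or intercurrent events, with counts by arm.
3. **Sensitivity analysis.** Repeat the primary comparison without these patients.
4. **Consumption data.** State in advance how morphine consumption is handled for patients kept sedated or ventilated, since their patient-controlled use may not be measurable or may not reflect pain.

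The cost is a change of protocol wording and one further analysis. A few complicated cases stay in and may add variance, and the rule in item 4 has to be written. Whether remifentanil or support may be used is a clinical matter and is not addressed here.

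### The protocol names two primary outcomes, 72-hour and 24-hour morphine consumption, and its sample size supports only the 24-hour one

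*Protocol*

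**What the plan says.** The protocol's Outcome measures section, under Primary outcomes, argues that pain is worst in the first two to three days and concludes: "The primary outcome will be set at 72-hour time frame based on the postoperative morphine consumption".

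The section Sample size calculation and statistical methods says the calculation is "based on postoperative morphine consumption at 24 hours, which is the primary outcome variable". It gives pilot results at 24 hours, mean (SD) 21.5 (8.2) mg with methadone and 30.3 (14.0) mg with morphine, and continues: "With an alpha probability of 0.05 and a power of 90%, a sample size of 34 patients in each group will be needed". With 15% drop-out the total is set at 86.

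Data collection, chart item 5, extracts both: "Total morphine consumption at 24 and 72 hours after surgery". Secondary outcomes lists neither total.

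The background gives mixed signals about effects beyond the first day. Challenges in pain management expects "significant pain relief up to 1-2 days postoperatively" from a single dose. Gaps in the literatures cites a cardiac surgery trial against fentanyl and reports of its pain scores that "the severity of postoperative pain was decreased by 30-40% during the first three days after cardiac surgery". The opioid result it takes from the same trial covers one day only: "There was 40% reduction in morphine requirement during the first 24h after extubation".

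**The concern.** Two current sections each name a primary outcome, and they differ. A statistical analysis plan could choose one, but one of the protocol's two statements would still be wrong.

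Two things are at stake. First, the 90% power claim is attached to the 24-hour total. If the Primary outcomes section governs, the trial has no sample size justification for its primary outcome. Second, both totals will exist at analysis and the protocol supports calling either one primary. It does not plan to claim success on whichever total is significant, but its wording does not prevent this, and doing so at P<0.05 would generally push the type I error above 5%.

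**Working it through.** **Inputs** (Sample size calculation and statistical methods): 24-hour means 21.5 and 30.3 mg; SDs 8.2 and 14.0 mg; alpha 0.05, taken as two-sided because sidedness is not stated; 34 per group; 15% drop-out; total 86.

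**24-hour effect size**

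- Difference = 30.3 − 21.5 = 8.8 mg
- Pooled SD = √((8.2² + 14.0²)/2) = 11.47 mg
- Standardized difference d = 8.8/11.47 = 0.767

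**Reproducing the plan's figure.** For 90% power the normal approximation gives 36 per group and the noncentral t gives 37. The stated 34 comes out of the noncentral t if d is rounded to 0.8, or out of the normal formula if the two SDs are simply averaged to 11.1 mg. So 34 is close, and it is clearly a 24-hour calculation.

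**24-hour power** (two-sample noncentral t). The evaluable number is 34 per arm as stated, or about 37 from the total: 86 × 0.85 / 2 = 36.6.

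- 34 per arm: 87.6%
- 37 per arm: 90.2%

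**72-hour power.** The protocol has no 72-hour inputs, so no single figure can be computed. The table shows assumed multiples of the 24-hour difference and SD. With equal variance each day, SD ×1.73 (√3) corresponds to independent days and SD ×3 to fully correlated days. Power is at 37 per arm, with 34 per arm in brackets.

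| Assumed 72-hour difference | SD ×1.73 | SD ×2 | SD ×3 |
|---|---|---|---|
| 8.8 mg (unchanged) | 47% (44%) | 37% (34%) | 19% (18%) |
| 17.6 mg (×2) | 96% (95%) | 90% (88%) | 58% (55%) |
| 26.4 mg (×3) | >99% (>99%) | >99% (>99%) | 90% (88%) |

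Power holds when the difference grows at least as fast as the SD and falls otherwise. The protocol does not say which applies. With 34 evaluable per arm, 90% power needs a 72-hour standardized difference of about 0.80.

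**Type I error if success could be claimed on either total**, each tested at two-sided 0.05 (bivariate normal, assumed correlation r between the two test statistics):

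- r = 0.5: 9.1%
- r = 0.7: 8.3%
- r = 0.9: 7.0%

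The 24-hour total is part of the 72-hour total, so r is tied to the SD multiple. With equal-variance, equally correlated days, r = multiple/3:

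- SD ×1.73: r = 0.58, error 8.8%
- SD ×2: r = 0.67, error 8.5%
- SD ×3: r = 1, error 5.0%, so no inflation

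**Time zero (smaller point).** Chart item 5 counts the totals from surgery. Figure 1 places morphine consumption under columns timed from extubation. The Primary outcomes sentence gives no starting point.

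**The case against.** The contradiction itself is hard to dispute; the serious objections concern what is built on it.

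- **The power table uses no 72-hour data.** This is true. It shows only that the answer depends on figures the protocol does not give, and it is no evidence that the trial is underpowered.
- **The type I error is hypothetical.** Also true: no either-or claim is planned, and under the table's own SD scalings the range is about 5% to 8.8%. It is a consequence of loose wording, not of a stated analysis.
- **The background evidence is limited.** The 30-40% reduction over three days concerns pain severity in a comparison with fentanyl, so it says little about 72-hour morphine use against morphine. This supports treating 72-hour power as unknown.
- **Choosing 24 hours does not leave a clean calculation.** This stands. Power at 34 per group is 87.6%, and 34 per group with 15% drop-out gives 68/0.85 = 80, not 86. That needs its own correction.
- **Time zero is minor.** Chart item 5 does state a starting point, and Figure 1 is a visit schedule whose columns may be displaced in the text available here. It is a request for clarification.
- **The trial is called a pilot.** The label softens the consequence of unknown power, but the same document sets alpha 0.05, claims 90% power and plans significance tests.
- **Hierarchy and alpha rules can sit in an analysis plan.** They can, but the identity of the primary outcome is stated in this protocol, twice and differently.

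**Conclusion.** The point holds and must be fixed. The protocol names 72-hour consumption as primary in one section and 24-hour consumption in another, and nothing in it settles which governs. The stated 90% power refers to the 24-hour total only (87.6% at 34 evaluable per arm, 90.2% at 37). Power for the 72-hour total cannot be derived from the document: the assumed scenarios run from 18% to over 99%, and none is favoured by the text. If success were claimed on either total, the type I error would be 7.0% to 9.1% for correlations of 0.9 down to 0.5, falling to 5% as the correlation approaches 1. The contradiction and the absence of 72-hour planning values rest on no assumption. The power figures assume two-sided tests and approximately normal totals, and the 72-hour figures also rest on the assumed scalings.

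**What to change.** Before unblinding, name one window as the single primary outcome in both Primary outcomes and Sample size calculation and statistical methods, and list the other under Secondary outcomes.

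- **If 24 hours is primary:** change the Primary outcomes sentence. The existing sample size basis then applies, subject to the arithmetic points above.
- **If 72 hours is primary:** this fits the clinical reason the protocol gives. Replace the 24-hour inputs with 72-hour means and SDs, for example from the 50-patient pilot if it recorded them, and restate the power. Failing that, say plainly that the 90% does not apply to the primary outcome.

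Also state one time zero for the morphine total, end of surgery or extubation, in the outcome, data collection and sample size sections and in Figure 1. Anaesthesia and interventions says "Patient-controlled analgesia (PCA) morphine protocol will be prescribed to patients for 72 hours after operation for postoperative analgesia", so a total running to 72 hours after extubation would extend past that period; these passages must be reconciled.

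The cost is protocol wording, since both totals are already collected. One window becomes secondary, and if 72 hours is kept the restated power may be above or below 90%.
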